6.1.4 Analysis Methods

There will be no formal statistical testing unless indicated otherwise.

A summary will be provided for the following TEAEs overall (Table 14.3.1.1):

- Subjects with Any TEAE
- Subjects with Any Study Drug-Related TEAE
- Subjects with Any TEAE with an Outcome of Death
- Subjects with Any Serious TEAE
- Subjects with Any Study Drug-Related Serious TEAE
- Subjects with Any TEAE Leading to Discontinuation of Study Drug
- Subjects with Any Study Drug-Related TEAE Leading to Discontinuation of Study Drug
- Subjects with Any TEAE of Special Interest
- Subjects with Any Study Drug-Related TEAE of Special Interest

The adverse events will be shown by MedDRA system organ class and preferred term, in order of descending overall frequency. For each AE, the percentage of subjects who experience at least 1 occurrence of the given event will be

summarized. Incidence tabulations will be provided for overall summary (Table 14.3.1.2.1-14.3.1.2.2), summary by highest severity (Table 14.3.1.3), and summary by relatedness (Table 14.3.1.4).

Incidence of Serious TEAEs, TEAEs of Special Interest, TEAEs Leading to Subject Withdrawal and TEAEs Leading to Death will be tabulated by MedDRA System Organ Class and Preferred Term (Table 14.3.1.5.1-14.3.1.5.4) and listed as well (Listing 14.3.1.6.1-14.3.1.6.4).

Adverse events with preferred terms associated with blood pressure changes will also be presented by infusion period, SOC, PT, and treatment group. Infusion period will be further categorized by whether the event start date occurred during the infusion period or after the infusion period. Examples of such events can be identified by the following preferred terms: blood pressure decreased, blood pressure diastolic decreased, blood pressure systolic decreased, blood pressure increased, increased blood pressure, blood pressure diastolic increased, blood pressure systolic increased, hypotension, hypertension, low blood pressure, high blood pressure. This is a non-exhaustive list and a review of AE MedDRA coding will be conducted prior to lock to identify all events associated with blood pressure changes (Table 14.3.1.5.5.).

6.2 Clinical Laboratory Evaluations

Numeric measurements of hematology, serum chemistry, and urinalysis will be investigated. Changes from baseline for all safety lab parameters will be summarized at each scheduled timepoint (Table 14.3.2.1.1-14.3.2.1.3). Shift tables from the baseline to each post-baseline scheduled timepoint will be presented (Table 14.3.2.3.1-14.3.2.3.3).

6.3 Vital Signs

Summary statistics will be presented for the actual values and change from baseline values (as appropriate) at each time point for all vital signs (Oral Temperature, Pulse Rate, Systolic Blood Pressure, Diastolic Blood Pressure, Respiration Rate) and weight. Changes from baseline for all vital sign parameters and weight will include pre-dose at Day 1 to pre-dose at subsequent days as well as timepoints during infusion (Table 14.3.3.1). In addition, changes from baseline for all vital sign parameters will include pre-dose at each infusion day to all post-dose timepoints within each infusion day (Table 14.3.3.2).

The incidence of the following blood pressure changes will be summarized (Table 14.3.3.3):

- Systolic BP > 180
- Systolic BP > 200
- Systolic BP < 90
- Diastolic BP > 110

- Diastolic BP > 120
- Diastolic BP < 50
- A change of >30% from Day 1 pre-dose (baseline) in systolic and/or diastolic BP. This change includes positive and negative percent changes.

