5.2 EXCLUSION CRITERIA

An individual will not be eligible for inclusion if any of the following criteria apply:

1. Evidence of clinically relevant neurological disorder(s) other than probable AD.
2. History of coagulation disorders or hypercoagulability; any concurrent use of an anticoagulant therapy (e.g., heparin, warfarin, thrombin inhibitors, Factor Xa inhibitors). Use of antiplatelet drugs (e.g., aspirin or clopidogrel) is allowed.
3. Prior hypersensitivity reaction to any human blood product or intravenous infusion; any known clinically significant drug allergy.
4. Treatment with any human blood product, including transfusions and intravenous immunoglobulin, during the 6 months prior to Screening.
5. History of immunoglobulin A (IgA), haptoglobin or C1 inhibitor deficiency.
6. History of anaphylaxis or thromboembolic events as a complication of intravenous immunoglobulins.
7. Unstable coronary heart disease, e.g. myocardial infarction or severe or unstable angina in the 6 months prior to dosing.
8. Clinically significant abnormalities on echocardiogram.
9. Moderate to severe congestive heart failure (New York Association Class III or IV).
10. Poorly controlled high blood pressure (systolic blood pressure of 160 mmHg or higher and/or diastolic blood pressure of 100 mmHg or higher) despite treatment during the 3 months prior to dosing, or treatment-refractory high blood pressure, defined as treatment requiring 3 or more antihypertensives from different classes.
11. History of Torsades de Pointes dysrhythmia.
12. Clinically significant abnormalities on screening ECG including QTc intervals (using Fridericia's correction formula) of ≥ 450 ms in men and ≥ 470 ms in women.
13. History of hypocalcemia of any kind, including secondary to absorption syndromes secondary to gastric bypass surgery.
14. Clinically significant liver disease or biliary abnormalities.
15. Uncontrolled diabetes defined as HbA1c $>7.5\%$.
16. Malignancy for which the subject has undergone resection and/or radiation and/or chemotherapy in the past 3 years; treated basal cell carcinoma and/or fully cured squamous cell carcinoma is allowed.
17. Clinically significant abnormalities in complete blood count, complete metabolic panel, serum albumin, blood coagulation tests, or the levels of thiamine, pyridoxine, cobalamin and thyroid stimulating hormone.

18. Hemoglobin <10 g/dL in women and <11 g/dL in men.

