2.3 Study Phase, Visit, and Day

The study is set up as shown above, along with study phase, visit, and day. In general, the baseline is defined as the last assessment before the first intake of the study medication unless otherwise specified. All scheduled assessments after first administration of study drug will be used.

Repeat/unscheduled assessments will not be used in descriptive statistics or any per-time point analyses but will be shown in listings as applicable. Pre-dose unscheduled assessments will be taken into account for baseline determination and post first dose unscheduled assessments will be taken into account for worst-case determination as applicable.

Reference date refers to the start date of the first study drug administration. All efficacy and safety assessments at all visits will be assigned a day relative to this date. The relative day will be defined as: visit date – reference date + 1 for visits on or after the reference date and visit date – reference date for visits before the reference date. Consequently, there is no 'Day 0' defined.

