8 CHANGES FROM PROTOCOL

The Per Protocol dataset is defined in the protocol as: a subset of the Evaluable Dataset comprised of subjects who have no Major Protocol Deviations. All failed eligibility criteria are considered a Major Protocol Deviation, however, not all eligibility criteria failures should automatically remove a subject from the Per Protocol dataset. This SAP clarifies which protocol deviations will exclude a subject from the per protocol dataset and all protocol deviations will be reviewed by the study team prior to database lock to identify the final Per Protocol dataset definition

Blood pressure values that constituted an AESI were at the discretion of the PI. As such, ranges for blood pressures of special interest (BPSI) were identified and will be analyzed according to section 6.3

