Table 14.3.2.1.2	Changes in serum chemistry measurements	SAF
Table 14.3.2.1.3	Changes in urinalysis measurements	SAF
Table 14.3.2.3.1	Shift Table in hematology measurements	SAF

Number	Title	Population
Table 14.3.2.3.2	Shift Table in serum chemistry measurements	SAF
Table 14.3.2.3.3	Shift Table in urinalysis measurements	SAF
Table 14.3.3.1	Changes from baseline in vital sign measurements and weight	SAF
Table 14.3.3.2	Changes from pre-dose in vital sign measurements within each infusion day	SAF
Table 14.3.3.3	Blood pressure changes of special interest	
Table 14.3.4.1	Changes from baseline in ECG measurements	SAF
Table 14.3.4.2	Frequency of overall ECG results	SAF
Table 14.3.5.1	Frequency of abnormal physical examination results	SAF
Table 14.3.5.2	Shift Table in physical examination results	SAF

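### Table 14.3.3.3 counts absolute blood-pressure values as changes without a baseline condition, so a subject already below SBP 90 or DBP 50 before dosing and still below it afterwards is counted

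*SAP*

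**What the plan says.** SAP 6.3 announces an incidence table: "The incidence of the following blood pressure changes will be summarized (Table 14.3.3.3". The rows are SBP above 180, SBP above 200, "Systolic BP < 90", DBP above 110, DBP above 120, "Diastolic BP < 50", and a relative row: "A change of >30% from Day 1 pre-dose (baseline) in systolic and/or diastolic BP". The relative row is a separate criterion, not a condition on the other six.

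The table list in SAP section 10 titles the output "Blood pressure changes of special interest". SAP section 8 describes the same items differently: "ranges for blood pressures of special interest (BPSI) were identified and will be analyzed according to section 6.3".

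SAP 2.3 gives the general rule on which readings enter the analysis: "All scheduled assessments after first administration of study drug will be used". It adds that unscheduled readings after the first dose count towards worst-case values. It sets no baseline condition for the limits.

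On eligibility, exclusion criterion 10 in Protocol 5.2 covers poorly controlled hypertension, with a numeric limit: "systolic blood pressure of 160 mmHg or higher and/or diastolic blood pressure of 100 mmHg or higher". No criterion gives a numeric lower limit.

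**The concern.** The table's name and its content do not match. An incidence of changes suggests something that arose after dosing; six of the seven rows record only that a value lay in a range.

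The documents use a baseline or worsening reference for comparable safety outputs. Treatment-emergent events must be reported or have worsened once dosing starts (SAP 6.1.2), laboratory values get shift tables from baseline (SAP 6.2), and physical examinations get a shift from Day 1 pre-dose (SAP 6.5). The absolute blood-pressure rows have no such reference.

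This matters most for low values. Protocol 2.3.1 names a fall in blood pressure as a possible effect of infusion, so readers will look at the low rows for a signal. In arms this small, one subject with habitually low pressure can create or mask a visible difference unrelated to the infusion.

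**Working it through.** The plan states no expected figure for this table, so there is nothing to reproduce. The check applies the written rules to example subjects and then sizes one miscounted subject.

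**1. The rules applied.** The values are illustrative. The change is (post − pre)/pre. Newly past means pre-dose inside the limit and post-dose beyond it.

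| Pre-dose → post-dose | Change | Counted in absolute row | Counted in >30% row | Newly past limit |
|---|---|---|---|---|
| SBP 88 → 88 | 0.0% | yes | no | no |
| SBP 86 → 88 | +2.3% | yes | no | no |
| DBP 48 → 48 | 0.0% | yes | no | no |
| SBP 92 → 89 | −3.3% | yes | no | yes |
| SBP 130 → 89 | −31.5% | yes | yes | yes |
| DBP 52 → 49 | −5.8% | yes | no | yes |
| SBP 88 → 95 at all later readings | +8.0% | no | no | no |

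The first three subjects are counted without any fall. The table cannot tell them from the next three. The last is not counted, because SAP 2.3 directs attention to readings after the first administration.

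**2. Which rows are exposed.** The four high limits (180, 200, 110, 120) all lie above the 160/100 in exclusion criterion 10. A pre-dose value beyond them is less likely, though not impossible. The two low limits have no matching eligibility limit.

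**3. Size of one subject.** About 20 subjects at 2:1 (SAP 1.3) gives roughly 13 and 7. One subject is 1/13 = 7.7 points on GRF6019 or 1/7 = 14.3 points on placebo.

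**4. Chance that someone starts low.** The documents give no blood-pressure distribution, so every figure here is an assumption. The formula is 1 − (1 − p)^20, with p the proportion starting below a limit.

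- p = 2%, 5%, 10%, 15% gives 33%, 64%, 88%, 96%.
- If pre-dose DBP is normal with mean 70 and SD 8, 10 or 12, the chance that at least one of 20 starts below 50 is 11.7%, 36.9% or 62.4%. With mean 75 it is 1.8%, 11.7% or 31.3%.

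These are chances of starting low. Being counted also needs a low reading after dosing, so they are upper bounds on the chance of a miscount of this kind.

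**5. Would counting only new crossings be safe?** SBP 88 falling to 64 is −24/88 = −27.3%. DBP 48 falling to 35 is −13/48 = −27.1%. Under a new-crossings-only rule both leave their absolute row, and neither reaches the >30% row. A real fall would appear in no row.

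**The case against.** The strongest reply is that SAP section 8 calls these items ranges. Counting values in a flagged range by randomized arm is a coherent display, so only the label is loose. Other outputs supply the baseline view: Table 14.3.3.1 (change from Day 1 pre-dose), Table 14.3.3.2 (change from each infusion day's pre-dose), the analysis of blood-pressure adverse events in SAP 6.1.4, and Listing 16.2.9, where about 20 subjects can be read one by one. There is no formal testing, and no halting rule in Protocol 8.5 cites the table.

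Much of this stands. It makes the point minor and supports keeping the existing counts. It does not remove the gap: Tables 14.3.3.1 and 14.3.3.2 are group summaries, the adverse-event analysis depends on what was reported, and the listing requires reconstruction by hand. No planned table separates new crossings from values that were already low.

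Three stronger readings are tempting, and the documents do not support them:

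- **A low pre-dose value alone puts a subject in the table.** SAP 6.3 does not repeat which readings count, but the general rule in SAP 2.3 uses assessments after first administration. A later reading must also be past the limit.
- **All six absolute rows are equally affected.** The 160/100 exclusion makes the high rows much less exposed.
- **The table displaces investigator reporting.** SAP section 8 says that ranges were identified and will be analysed; reported adverse events and events of special interest are still tabulated under SAP 6.1.4.

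**Conclusion.** The concern holds as a minor defect of definition. The absolute rows mix subjects who crossed a limit after dosing with subjects who were past it from the start and stayed there, and the word changes invites readers to treat both as effects of infusion. The practical exposure is in the SBP <90 and DBP <50 rows.

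One such subject moves an arm by about 7.7 or 14.3 points, assuming a 13/7 split with everyone treated. How likely this is cannot be settled from the documents: the DBP model alone spans about 2% to 62%, and no SBP distribution was modelled. The conclusion rests on the wording of the rule, not on those probabilities. It does not question the limits themselves.

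**What to change.** In SAP 6.3, keep for each absolute limit the number and percentage of subjects with any reading past it after the first administration. Beside it, by arm, add:

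- (a) the number already past the limit at Day 1 pre-dose;
- (b) the number newly past the limit after dosing, with the Day 1 pre-dose value inside it.

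Where every subject has a Day 1 pre-dose reading, the existing count minus (b) is the number who started past the limit and had at least one later reading past it. Already-low subjects who worsen stay in the existing count.

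Do not replace the rows with (b) alone, for the reason in step 5 of the working. Do not reset the reference to each day's pre-dose value for the main count: a subject who first falls below 90 on Day 2 and is still low before the Day 3 infusion would then drop out of the Day 3 count. State in 6.3 that the general rule of SAP 2.3 on readings after first dosing applies, and title the absolute rows as values rather than changes.

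The cost is a few words in the SAP, a small amount of programming on data already collected, and a wider table.

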2.3 POTENTIAL RISKS AND BENEFITS

2.3.1 KNOWN POTENTIAL RISKS

Collected human plasma may be used as a therapeutic product (known as “plasma” or “fresh frozen plasma”) or as source material for the production of pharmaceutical fractionated products (known as “plasma products” or “plasma derivatives”) (Burnouf 2007). GRF6019, a [REDACTED] human plasma protein fraction, [REDACTED] serves as a viable source of soluble, infusible plasma proteins from [REDACTED] healthy donors. [REDACTED]

[REDACTED] ABO antigen typing is not required prior to administration. Finally, the additional steps taken during production to remove viral pathogens provide an increased margin of pathogen safety in comparison to fresh frozen plasma.

[REDACTED] GRF6019 is not expected to significantly alter the urinalyses of recipients, their bleeding times, coagulation times, prothrombin times, prothrombin consumption, platelet counts or fibrinogen levels when given in quantities of up to 1000 mL. Decreased blood pressure may occur, particularly following rapid infusion. The blood pressure may normalize spontaneously after the slowing or discontinuation of the infusion. [REDACTED]

GRF6019 is made from human plasma and may carry a risk of transmitting infectious agents, e.g., viruses, the variant Creutzfeldt-Jakob disease (vCJD) agent, and, theoretically, the Creutzfeldt-Jakob disease (CJD) agent. The risk that GRF6019 can transmit an infectious agent has been reduced by screening plasma donors for prior exposure, testing donated plasma, and including manufacturing steps with the capacity to inactivate and/or remove pathogens.

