7.3.4 TREATMENT

The treatment period includes a total of 5 infusions during Week 1. It is anticipated that sites will infuse subjects with 5 doses over 5 days. A “grace day” is allowed in the event of unanticipated safety or health concerns during the treatment period.

Visits 3 -7 (Days 1-5)

- Perform the following procedures prior to administering study treatment:
 - Review AEs and concomitant medications.
 - Obtain samples for proteomics/epigenetics/biobanking; fasting samples preferred (**Visit 3 Only**).
 - Obtain sample for ApoE genotype testing (**Visit 3 Only**).
 - Obtain pre-infusion safety laboratory samples and assess results **prior to the next day's infusion (Visits 4, 5, and 6 Only)**. (When using an i-STAT Handheld Blood Analyzer, the blood sample(s) may be obtained on the same day as the infusion, provided that all pre-infusion safety lab results are available and interpreted prior to the subject's infusion start on Visits 5, 6, and 7.)
 - Collect urine for urinalysis (**Visit 6 Only**).
 - Measure and record the subject's weight in kilograms.
 - Perform targeted physical exam (i.e. auscultation of heart and lungs and assessment of peripheral edema) (**Visits 3, 5, and 7 Only**).
 - Perform 12-lead ECG (**Visits 3 and 5 Only**).
 - Collect pre-infusion vital signs.
- Administer study treatment and perform safety assessments per the Infusion Administration Manual.

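### The >30% blood-pressure count in SAP 6.3 uses only the Day 1 pre-dose value, so on Days 2–5 it mixes day-to-day drift with the infusion response; a same-day row is missing

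*SAP*

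**What the plan says.** SAP 6.3 plans three blood-pressure outputs.

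- **Table 14.3.3.1** summarises change from Day 1 pre-dose, both to later pre-dose values and to readings during infusion.
- **Table 14.3.3.2** uses a same-day reference: "changes from baseline for all vital sign parameters will include pre-dose at each infusion day to all post-dose timepoints within each infusion day". The list of tables in SAP Section 10 titles it "Changes from pre-dose in vital sign measurements within each infusion day", for the Safety set. Under SAP 2.6 it will show means, SDs, medians, minima and maxima.
- **Table 14.3.3.3** gives incidences. It has six absolute limits, of which the low ones are "Systolic BP < 90" and "Diastolic BP < 50", and one relative criterion: "A change of >30% from Day 1 pre-dose (baseline) in systolic and/or diastolic BP". On direction the SAP adds: "This change includes positive and negative percent changes". It does not say which timepoints enter this table.

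On risk, Protocol 2.3.1 says: "Decreased blood pressure may occur, particularly following rapid infusion". For Visits 3 to 7, Protocol 7.3.4 instructs sites: "Collect pre-infusion vital signs". A footnote to the schedule of events (Protocol 15.1) requires further readings during each infusion and for 2 hours afterwards, on a schedule held in a separate manual. SAP Section 8 explains that the investigator decided which pressures counted as events of special interest, and that fixed ranges were therefore defined for analysis.

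**The concern.** The expected reaction is acute and belongs to a particular infusion, so the natural reference for counting it is the reading taken just before that infusion. Table 14.3.3.2 follows this logic for its summary statistics. The incidence row does not: on Days 2–5 it compares with a reading taken one to four days earlier. The row then measures two things at once, namely how far resting pressure has drifted since Day 1 and how far pressure moved during the infusion.

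This matters because safety is the primary objective and Table 14.3.3.3 is the fixed-threshold output, meant not to depend on what an investigator chose to report. It holds the only relative-change count per subject. With about 20 subjects randomised 2:1 (about 13 and 7), a modest excess of infusion-day changes on GRF6019 is easily hidden by flags that come from drift.

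**Working it through.** The plan states no expected rate for this criterion, so there is no figure to reproduce. The check has three steps.

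**1. When the two references disagree.** Let B be Day 1 pre-dose, P that day's pre-dose, and f the fall from P as a fraction. The nadir is P(1 − f). The Day 1 rule flags the fall only if P(1 − f) < 0.70 B, so it misses it when P/B ≥ 0.70/(1 − f).

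| Same-day fall f | Missed when P/B is at least | Pre-dose above Day 1 by |
|---|---|---|
| 31% | 0.70/0.69 = 1.014 | 1.4% |
| 35% | 0.70/0.65 = 1.077 | 7.7% |
| 40% | 0.70/0.60 = 1.167 | 16.7% |
| 45% | 0.70/0.55 = 1.273 | 27.3% |

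If pre-dose readings also count, P/B > 1.30 is itself flagged, as a rise. The window for missing a 35% fall is then 1.077 to 1.30. A miss always needs an upward drift of pre-dose pressure, and larger falls need a larger drift.

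**2. Worked cases (Day 1 pre-dose / Day 4 pre-dose / Day 4 nadir).**

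- *Missed.* Systolic 120/150/100: (100 − 150)/150 = −33.3% same-day, (100 − 120)/120 = −16.7% from Day 1. Diastolic 80/95/60: −36.8% same-day, −25.0% from Day 1. The pre-dose rises are +25% and +18.8%, and no absolute limit is crossed. Nothing in Table 14.3.3.3 records this subject.
- *Flagged without an infusion change.* Systolic 150/110/104: (104 − 110)/110 = −5.5% same-day, (104 − 150)/150 = −30.7% from Day 1.

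The low systolic limit helps only at lower starting values. Any fall above 30% from a pre-dose of 128 or less ends below 90 (128 × 0.70 = 89.6). A 31% fall from above about 130 does not (90/0.69 = 130.4).

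**3. Simulation under assumed variability.** The documents give no means, SDs or number of readings, so all inputs here are assumptions: 40,000 subjects, 5 infusion days, mean 135/75 mmHg, systolic–diastolic correlation 0.6. SDs are given as between-day/within-day. Set A uses 4 to 8 readings a day, and its Day 1 rate also counts follow-up visits. Set B uses 8 readings a day on infusion days only. The last two columns show the share of subjects with at least one >30% flag when there is no drug effect.

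| Set | Systolic SDs | Diastolic SDs | Day 1 reference | Same-day reference |
|---|---|---|---|---|
| A low | 7/5 | 4/4 | 9% | 0.7% |
| A middle | 10/7 | 6/5 | 45% | 9% |
| A high | 13/9 | 8/6 | 83% | 36% |
| B low | 6/6 | 4/4 | 12% | 3% |
| B middle | 10/8 | 6/5 | 50% | 16% |
| B high | 14/10 | 8/7 | 87% | 62% |
| B mostly between-day | 14/4 | 8/3 | 48% | <1% |

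At a middle rate of 45–50%, drift and reading noise alone would flag about 6 of 13 active subjects (13 × 0.45 = 5.9) and about 3 of 7 on placebo (7 × 0.45 = 3.2).

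For misses, Set B was given a Day 4 fall averaging 30%, 35% or 40% in both pressures. Among readings with a systolic same-day fall above 30%, the Day 1 rule missed 6–43% on systolic alone and 3–29% on systolic or diastolic. With the <90 and <50 limits added, 1–19% stayed unflagged. A same-day rule flags all of them by definition.

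**The case against.** The strongest case for the plan has four parts.

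- **The row may be meant to measure something else.** The SAP calls it a change from baseline, not an infusion change. Day 1 pre-dose is the last untreated value and fits the general baseline definition in SAP 2.3, whereas pre-dose on Days 2–5 follows earlier infusions. Counting cumulative departure over five daily infusions is legitimate. This stands, and it is why the row should stay.
- **Other outputs show same-day falls.** Table 14.3.3.2 shows the largest fall in each arm, SAP 6.1.4 tabulates blood-pressure adverse events by infusion period, and Listing 16.2.9 gives every reading. With about 20 subjects the falls could be found by hand. This largely stands, but none of these is a count against a fixed threshold. The adverse-event table depends on what was reported, and its number, 14.3.1.5.5, does not appear in the Section 10 list.
- **The size is driven by assumptions.** The simulated ranges are very wide, and at high within-day noise the same-day rule still flags up to 62%. Changing the reference does not remove reading noise. This stands.
- **The consequence is limited.** The safety analysis is descriptive, and noise arises in both randomised arms. This also stands.

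**Conclusion.** The point holds in a limited form. The only >30% count is tied to one Day 1 value. On Days 2–5 it can therefore flag subjects with little same-day change and leave out some with a same-day fall above 30%. No planned table counts the latter, although the readings exist. The algebra and worked cases rest on no assumptions. The rates rest entirely on assumed variability and reading counts and should be read as a range, not an estimate. The effect on the group comparison is dilution in both arms.

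Three stronger readings are tempting and are not supported.

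- A reader might infer that the plan misses infusion-related falls on Days 2–5. In the simulation the Day 1 rule still caught 57–94% of systolic falls above 30% on systolic pressure alone, and more once diastolic pressure and the absolute limits were counted.
- A reader might infer that every infusion-day reading is compared with Day 1. Table 14.3.3.1 makes this plausible, but the SAP does not state it for Table 14.3.3.3.
- A reader might infer a bias in favour of GRF6019. Nothing in the documents points in one direction.

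**What to change.** Add one row to Table 14.3.3.3: the number of subjects with a >30% change from the same day's pre-infusion value, using readings during and up to 2 hours after each infusion. State in SAP 6.3 which timepoints enter each row.

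Keep the Day 1 row unchanged in scope as the measure of cumulative change. Limiting it to pre-dose and follow-up readings would open a new gap. For systolic 140/112/92 (in the order used above), pre-dose is down 20%, the nadir is 18% below that day's pre-dose and 34% below Day 1, and it is not under 90. Only the Day 1 row, applied to infusion readings, records it.

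The cost is one derived variable, one table row and a sentence of SAP text before database lock. No new data are needed, and no threshold changes.

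### The >30% blood-pressure row in Table 14.3.3.3 combines rises with falls and systolic with diastolic, so it does not show the direction that the protocol names as a risk

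*SAP*

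**What the plan says.** SAP 6.3 lists seven blood-pressure criteria whose incidence goes into Table 14.3.3.3. Six each concern one pressure and one direction. Four are high values (systolic above 180 and 200, diastolic above 110 and 120) and two are low: "Systolic BP < 90" and "Diastolic BP < 50". The seventh is a relative change: "A change of >30% from Day 1 pre-dose (baseline) in systolic and/or diastolic BP". The next sentence reads: "This change includes positive and negative percent changes". The SAP asks for no split of this criterion by direction or by pressure.

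SAP section 8 explains why the table exists. Which blood-pressure values counted as an adverse event of special interest had been left to the investigator. It continues: "As such, ranges for blood pressures of special interest (BPSI) were identified and will be analyzed according to section 6.3".

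Protocol 2.3.1 states the risk: "Decreased blood pressure may occur, particularly following rapid infusion". Parts of that section are blacked out; the readable text mentions no rise.

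**The concern.** The trial's primary objective is safety and tolerability, and the readable risk statement has a direction. Table 14.3.3.3 is the tabulated count of blood-pressure excursions against fixed limits, and it supplements a judgement left to investigators. In its only relative-change row, a subject whose systolic pressure fell by a third and a subject whose diastolic pressure rose by a third count alike. A reader who sees the row by arm cannot tell how much of it is the named risk. Rises unrelated to the product add to both arms and make the contrast in falls look smaller.

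**Working it through.** The plan gives no figure for this row, so there is none to reproduce. Two checks apply.

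**1. Do the two low rows already count every fall above 30%?**

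Inputs: the limits of 90 and 50 and the 30% threshold, all from SAP 6.3. A 30% fall from baseline B ends at 0.7 × B, so it stays at or above limit L when B ≥ L / 0.7.

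- Systolic: 90 / 0.7 = 128.6
- Diastolic: 50 / 0.7 = 71.4

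The fall needed to reach the limit is 1 − L / B:

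| Baseline | Value after a 30% fall | Fall needed to reach the limit |
|---|---|---|
| Systolic 120 | 84 | 25.0% |
| Systolic 130 | 91 | 30.8% |
| Systolic 140 | 98 | 35.7% |
| Systolic 159 | 111.3 | 43.4% |
| Diastolic 70 | 49 | 28.6% |
| Diastolic 80 | 56 | 37.5% |

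Below about 129 systolic or 72 diastolic, the low rows catch every fall above 30%. Above those values they miss some: from 140 systolic, a fall between 30% and 35.7% appears only in the combined row. Such baselines are eligible, because exclusion criterion 10 in Protocol 5.2 sets its limits for poorly controlled pressure at 160 systolic and 100 diastolic.

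The high rows have the same gap for rises: 180 / 1.3 = 138.5 systolic and 110 / 1.3 = 84.6 diastolic. Up to those baselines, a 30% rise does not exceed the lowest high limit.

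**2. How much does combining directions blur a difference in falls?**

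Assumptions (the documents give no such rates): falls above 30% in 30% of active and 10% of placebo subjects, with rises independent of falls within a subject. The combined rate is 1 − (1 − fall rate) × (1 − rise rate). Allocation from SAP 1.3: 20 × 2/3 ≈ 13 active and 20 × 1/3 ≈ 7 placebo. The last column is an exact binomial calculation at 13 versus 7.

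| Rises, active / placebo | Combined, active / placebo | Difference | Ratio | Chance that the active proportion is higher |
|---|---|---|---|---|
| Falls only | 30% / 10% | 20 points | 3.00 | 0.90 |
| 10% / 10% | 37% / 19% | 18 points | 1.95 | 0.84 |
| 20% / 20% | 44% / 28% | 16 points | 1.57 | 0.78 |
| 30% / 30% | 51% / 37% | 14 points | 1.38 | 0.74 |
| 10% / 30% | 37% / 37% | 0 points | 1.00 | 0.52 |

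Example, second line: active 1 − 0.7 × 0.9 = 0.37; placebo 1 − 0.9 × 0.9 = 0.19.

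Equal rises dilute the contrast but do not remove it. It disappears only in the last line, where rises are three times as common on placebo.

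**The case against.** The strongest reply is that falls are reported in several other places, and this is true.

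- Tables 14.3.3.1 and 14.3.3.2 summarise signed change for each vital sign separately, with mean, median, minimum and maximum by arm (SAP 2.6). For Table 14.3.3.2, "changes from baseline for all vital sign parameters will include pre-dose at each infusion day to all post-dose timepoints within each infusion day". A same-day reference suits a risk tied to rapid infusion better than a Day 1 reference does.
- Table 14.3.1.5.5 (SAP 6.1.4) presents blood-pressure adverse events by preferred term, and the example terms separate decreases from increases.
- Listing 16.2.9 shows the vital signs. With about 20 subjects, each fall can be traced.

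What remains is narrow. Change summaries do not count subjects beyond 30%, adverse-event terms depend on what is reported, and a listing is not a tabulation by arm.

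The table is also two-sided by design, with four high limits and two low ones, and section 8 gives it no direction. So it cannot be said that this row was intended to track decreases alone. The mock shells are a separate document and may already split the row, though the SAP does not require it.

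Two stronger readings are tempting:

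- A reader might infer that an excess of falls on active could vanish from the report. In this row that needs extra rises on saline placebo, for which the documents give no basis. The other outputs would still show the falls.
- A reader might infer that repeated readings make the row mostly noise. SAP 6.3 does not say whether incidence is per time point or over all readings, and the infusion-day schedule is in a manual outside these documents. A no-effect simulation (assumed baseline 130/75, SDs 10 and 8, systolic–diastolic correlation 0.6, 30 readings) flags 0.50 of subjects if readings are independent. With serial correlation of 0.8 or 0.9 the figure is 0.30 or 0.18. It is too dependent on assumptions to carry a conclusion. The noise also comes from comparing many readings with one baseline, not from combining directions.

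**Conclusion.** The point holds for one row of seven. The relative-change criterion does not show direction or which pressure changed, and the two low rows do not fill the gap for baselines of about 129 systolic or 72 diastolic and above. No other planned table gives the number of subjects per arm with a fall above 30%. This threshold result rests only on the SAP's own limits.

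The consequence is mainly dilution. Under the assumed fall rates and equal rises, the ratio drops from 3.0 to between 1.95 and 1.38, and the difference loses 2 to 6 of its 20 points. These sizes depend on assumed rates and on independence of rises and falls. The documents do not support saying that falls are hidden from the report.

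The row is descriptive, and the specific triggers in Protocol 8.5 do not refer to it. Sample size and error rates are unaffected. This is an optional improvement in reporting.

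**What to change.** In SAP 6.3, keep the 30% threshold and the Day 1 pre-dose baseline, and replace the single criterion with four rows in Table 14.3.3.3:

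- systolic decrease above 30%
- systolic increase above 30%
- diastolic decrease above 30%
- diastolic increase above 30%

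State that each row counts subjects with at least one such reading, by arm. This also settles how incidence is counted.

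The cost is three extra table rows from data already collected. The downside is sparse counts at about 13 versus 7 subjects. Splitting also leaves the background flags that come from repeated readings against one baseline, so the rows should be read with the signed change tables.
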